5.7 Criteria for Removal from Study

Participants will be removed from study if they withdraw consent or if they do not start vaccination by day+60* after HSCT as specified in the protocol. The reason for study removal and the date the participant was removed will be documented in the patient's medical record

* Day 60 or next business day, if day 60 occurs on a weekend or holiday

6.0 EXPECTED TOXICITIES AND DOSING DELAYS/DOSE MODIFICATIONS

Dose delays will be made using the following recommendations. Toxicity assessments will be done using NCI Common Terminology Criteria for Adverse Events (CTCAE) version 5.0 which is identified and located on the CTEP website at:

https://ctep.cancer.gov/protocolDevelopment/electronic_applications/docs/CTCAE_v5_Quick_Reference_5x7.pdf

All adverse events experienced by participants will be collected from the time of the first vaccination, through the study and until the final study visit (18 months from SCT). Participants continuing to experience toxicity at the off study visit will be contacted for additional assessments until the toxicity has resolved or is deemed irreversible.

6.1 Anticipated Toxicities

A list of the adverse events and potential risks associated with the GVAX vaccination administered in this study appear below and will determine whether dose delays and modifications will be made or whether the event requires expedited reporting **in addition** to routine reporting.

- 6.1.1 Anticipated toxicities of GVAX vaccine:
 - 6.1.1.1 **Localized skin reaction**: In previous studies using GM-CSF secreting tumor cell vaccines, little toxicity other than injection site discomfort was observed. The most common adverse events were injection site reaction with erythema, induration, and local pruritis that was easily controlled with topical emollients. Grade I fatigue and nasal congestion were occasionally noted. No organ toxicities or autoimmune events were noted. GVAX is an investigational product and may have other side effects that are unknown at this time.
 - 6.1.1.2 **Potential toxicities of GM-CSF**: GM-CSF is widely used for accelerating hematopoietic recovery and its spectrum of toxicity well established. It is likely that the highest level of GM-CSF secreted by the cells in the vaccine will be far lower than the usual starting dose for systemic application (350 mcg/day). While we cannot predict the exact toxicities attributable to local secretion of GM-CSF delivered by adenoviral mediated gene transfer, toxicities observed from the previous trial were restricted to erythema, pruritus, and swelling. Local toxicities of GM-CSF protein injection have included pustular eruption, necrotizing vasculitis, erythema, pruritus, recall erythema at previous injection sites, general papular rash, and phlebitis. Systemic toxicities have included fever, bone pain, malaise, diarrhea, transient liver function test (LFT) abnormalities, leukopenia, leukocytosis, eosinophilia, arthralgia, dyspnea, fluid retention, serous effusions, and recrudescence of various auto-immune diseases.
 - 6.1.1.3 **Potential for prolonged survival of leukemia vaccine cells**: All GM-CSF transfected autologous vaccine cells used in this trial will be irradiated with 10,000 rads to ensure they will die after several days. It is thus unlikely, but theoretically possible, that some tumor cells can survive the radiation, secrete GM-CSF long-term, or even cause leukemia relapse. These events have not been observed in any of the prior studies using retroviral or adenoviral transfected autologous tumor cell GVAX. However, in another study using a different type of GVAX vaccine composed of K562 leukemia cells transfected with GM-CSF and mixed with autologous tumor cells (DFCI Protocol 08-160), there was one case where the GM-CSF secreting K562 cells persisted at the vaccine site, and resulted in severe eosinophilia that proved to be ultimately fatal. It should be noted that K562 cells are not being used in this trial.
 - 6.1.1.4 **Auto-immune diseases**: This is a theoretic possibility for which patients will be monitored. In principle, the mechanisms that allow the immune system to recognize tumor antigens could also lead to breakdown of tolerance to normal or self-antigens, generating an autoimmune reaction. In the B16 murine melanoma model, vaccination with GM-CSF expressing tumor has been associated with depigmented patches of skin, an indication of tissue-specific autoimmunity. No examples of autoimmunity were seen in previous GVAX trials in AML, melanoma, renal cell carcinoma, prostate cancer, pancreatic cancer and lung cancer.
 - 6.1.1.5 **DMSO toxicity**. This toxicity is unlikely since the vaccine will be washed prior to administration. The cells are cryopreserved in 10% DMSO. DMSO is a hydrophilic

molecule, which diffuses through tissue rapidly. Although toxicities associated with intradermal administration of 10% DMSO in humans have not been published, toxicities associated with topical administration of 50% or more DMSO include skin irritation (vesiculation, urticaria, erythema, induration, pruritus, pain, bleeding, scaling, heat generation), garlic-like taste and odor on the breath and skin, transient disturbances of color vision, photophobia and diarrhea. The FDA has authorized the use of 50% DMSO for the treatment of interstitial cystitis in humans. Numerous studies in humans have demonstrated the relative safety of intravenous infusion of cells cryopreserved in 10% DMSO solutions, as this has become standard medical practice for infusion of cryopreserved peripheral blood and bone marrow stem cell collections in the setting of stem cell transplantation.

- 6.1.1.6 **Potential toxicity from Adenovirus Vector**. Wild type adenovirus serotype 5 (from which the vector used in this study is derived) is associated with an upper respiratory infection and conjunctivitis. There is controversy regarding a role in infantile intussusception. Other adenovirus serotypes are associated with cystitis, gastroenteritis, and pneumonia in military recruits during basic training. The adenoviral vector used in this study will be certified to contain less than one replication competent serotype 5 viral particles per vaccine inoculum. In the event that recombination between a latent wild type adenovirus and the introduced adenoviral vector occurs in the tumor cell, this will not lead to production of a replication competent GM-CSF expressing virus, as the GM-CSF cDNA is inserted in the E1 deleted region of the vector. Transduced cells will be injected into the skin; thus in the absence of an open wound, there is no significant risk of transmitting the virus to close contacts. If skin breakdown does occur, the skin should be covered with an adherent bandage until healing has occurred.
- 6.1.1.7 **Acute and chronic GVHD**. While we hypothesize that this vaccine may elicit a leukemia specific response by the donor immune system, the possibility that it may elicit or aggravate GVHD also exists. In our previous trial using this GVAX platform after RIC SCT (04-023), we did not observe any increase in acute or chronic GVHD in excess of what is expected at baseline. Differences in grade 3-4 acute GVHD between the vaccine and no vaccine arms will be assessed in planned interim analyses, see section 13.7.
- 6.1.1.8 **Unexpected vaccine related toxicity**: Any severe adverse event (CTC grade ≥ 3) that is not readily explained as a transplant or disease associated complication will be assessed as a possible vaccine related toxicity.

6.1.1.9 Anticipated Toxicities of Allogeneic transplantation

Fludarabine- The most common adverse events include myelosuppression (neutropenia, thrombocytopenia and anemia), fever and chills, infection, and nausea and vomiting. Other commonly reported events include malaise, fatigue, anorexia, and weakness. Serious opportunistic infections have occurred in CLL patients treated with fludarabine.

Busulfan- The most frequent, serious, toxic effect of busulfan is myelosuppression resulting in leukopenia, thrombocytopenia, and anemia. Hepatic veno-occlusive disease, which may be life-threatening, has been reported following the use of very high doses of busulfan in combination with cyclophosphamide or other chemotherapeutic agents prior to bone marrow transplantation. Possible risk factors for the development of hepatic veno-occlusive disease include: total busulfan dose exceeding 16 mg/kg based on ideal

body weight, high busulfan levels, and concurrent use of multiple alkylating agents. A clear cause-and-effect relationship with busulfan has not been demonstrated. At high doses, busulfan has been shown to induce clinical seizures, and as such, all patients will receive seizure prophylaxis during conditioning with high dose busulfan. Interstitial pulmonary fibrosis has been reported rarely. Busulfan is capable of inducing cataracts in rats and there have been several reports indicating that this is a rare complication in humans. In the few cases reported in humans, cataracts have occurred only after prolonged administration of busulfan. Hyperpigmentation is the most common adverse skin reaction and occurs in 5% to 10% of patients, particularly those with a dark complexion.

Tacrolimus - Primary toxicities include renal insufficiency, hypertension, hyperglycemia, hypomagnesemia, hypokalemia, and neurologic toxicity, including seizure and visual blindness. Rarely, tacrolimus may thrombotic microangiopathy, a severe condition characterized by acute renal failure, neurologic symptoms (confusion, seizures), anemia and thrombocytopenia.

Methotrexate- The primary toxicities expected are myelosuppression and mucositis. These effects are expected to be mild since dosing in mini-methotrexate is reduced. At high doses, MTX is also known to cause liver and/or renal damage. MTX can collect in extra-cellular fluid compartments, leading to delayed clearance and increased side effects. Therefore, in patients with significant third space fluid collections (e.g. ascites, pleural, pericardial effusions), leucovorin rescue may be administered at the discretion of the transplant physician.

GM-CSF- Short term administration of GM-CSF to hasten neutrophil recovery may lead to bone pain, back pain, headaches, and an elevated white blood cell count in the blood.

Pancytopenia- Pancytopenia is common and expected early after HSCT. If pancytopenia is prolonged, this may lead to infections, bleeding, or death. For patients with graft failure/prolonged pancytopenia, infusion of additional allogeneic stem cells or re-infusion of stored autologous stem cells (if available) will be considered. Patients who have not engrafted by day +45 will be removed from study and not receive vaccination.

Graft versus Host Disease (GVHD)- The principal target organs of acute GVHD are skin, gastrointestinal tract, and liver. Treatment in most cases will consist of increased doses of prednisone with or without the addition of other immune suppressive agents. Acute GVHD will be graded according to the modified Glucksberg score. ¹⁶ Chronic GVHD can also affect skin, gut, and liver, but in addition, can affect mucosal membranes (dry eyes, dry mouth, vaginal dryness), joints (stiffness), and lungs (dry cough, dyspnea). Chronic GVHD will be graded as limited or extensive based on the original Seattle criteria. ¹⁷

6.2 Toxicity Management

6.2.1 Vaccine site reaction- Local vaccine site reactions are generally transient and self limiting. Local management may include cold compress, moisturizing lotions. Topical steroids and/or topical antihistamines should be avoided if possible so as to not potentially blunt the

immunologic response to the vaccine. If the reaction persists more than 1 week, or the area of erythema and induration persists, a skin biopsy of the area will be considered.

6.2.2 Severe Eosinophilia- If increased absolute eosinophil count to > 5.0 x10^9/L (5000/ul) occurs during the vaccination period, further vaccines will be delayed (see section 5.3.4). In the event that the absolute eosinophil count remains >5.0 x10^9/L for more than 2 weeks despite being off vaccination, no further vaccinations will be given. Since mild eosinophilia is common after allogeneic HSCT, and is also a well recognized and expected response to vaccine, a transient increase in absolute eosinophil count is not an automatic cause for halting all future vaccinations.

6.3 Dose Modifications/Delays

There will be no vaccine dose adjustments for this study.

Guidelines for delays or discontinuation of vaccination are described in sections 5.3.3 and 5.3.4, respectively.

6.4 Unblinding

There are no plans for unblinding while patient are on treatment. Should an event occur where unblinding is believed to be necessary for the care of the patient, the case will be discussed with the study PI and [name]., the IND holder. After the study is closed to accrual and the last patient has completed the GVAX/placebo vaccinations, the study may be unblinded for data analysis.

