1.1 Study Design

GVAX vaccines will be generated by adenoviral vector mediated GM-CSF gene transfer into myeloblasts harvested from study subjects prior to admission for hematopoietic stem cell transplant Patients with Myelodysplastic syndromes (MDS) with excess marrow blasts or Acute myeloid leukemia (AML) not in remission are eligible. Leukemia cells will be harvested for vaccination generation after enrollment. Patients will be randomized (1:1) to GVAX versus placebo arm prior to The assignment of treatment arm will be blinded to the patients, treating transplant admission. physicians, nurses, research staff, and data assessors. Between the leukemia cell harvest and admission for allogeneic HSCT, patients are allowed to receive additional therapy (e.g. HMA therapy, chemotherapy etc.) at the discretion of the treating physician. Between day+30 to +60* after HSCT, patients with adequate hematologic recovery and no GVHD requiring systemic therapy will receive GVAX or placebo vaccine (normal saline) injections weekly x 3 week, then starting on week 5, every 2 weeks for 6 weeks, to complete a set of six total vaccinations. Patients will remain on tacrolimus for GVHD prevention during the vaccination period. Tacrolimus taper may commence after completion of vaccination, at the discretion of the treating physician, with the goal to be off immune suppression by 6-9 months post transplant in the absence of GVHD.

* Day 60 or next business day, if day 60 occurs on a weekend or holiday

1.2 **Primary Objective:**

Progression-free survival (PFS) at 18 months after randomization

1.3 Secondary Objectives:

- a) To assess the safety of vaccination following allogeneic (ablative or reduced intensity) stem cell transplantation
- b) To assess incidence of grade 2-4 and grade 3-4 acute GVHD, and chronic GVHD after vaccination following allogeneic stem cell transplantation.
- c) To assess PFS after start of vaccination
- d) To assess relapse and non-relapse mortality after vaccination
- e) To assess overall survival after vaccination
- f) To assess biologic activity of GVAX as compared to placebo vaccination after HSCT (see Section 8.0)

CONFIDENTIAL

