5.2.3.2 Methotrexate

For the RIC cohort (FluBu2)- The methotrexate dose will be 5 mg/m² IV on day+1,3,6,11, infused as per standard institutional guidelines. In cases where stem cell infusion (day 0) spans more than 1 day, the day +1 dose of methotrexate

should start 1 day after the end of the SC infusion.

For the Myeloablative cohort (FluBu4)- The methotrexate dose will be 15 mg/m² IV on day +1, and 10mg/m² on days +3,6, and 11. Methotrexate should be infused as per standard institutional guidelines. In cases where stem cell infusion (day 0) spans more than 1 day, the day +1 dose of methotrexate should start 1 day after the end of the stem cell (SC) infusion. Leucovorin rescue is allowed per standard practice guidelines if necessary, at the discretion of the transplant physician. The day 11 dose of MTX may be reduced 50% or omitted if deemed necessary based on the clinical situation, and at the discretion of the transplant physician. In cases where clinical toxicities, e.g. renal failure, pleural effusion, etc. would render completing at least 3 doses of methotrexate unsafe, substitution with mycophenolate mofetil (cellcept) 1000mg PO/IV BID or other agent such as sirolimus is allowed at the discretion of the treating physician. In instances where MTX is substituted by cellcept, it is recommended that the cellcept be discontinued around day +28 in the absence of GVHD.

5.2.4 Tacrolimus Taper:

- 5.2.4.1 Tacrolimus taper is NOT allowed during the vaccination period. Taper may commence 1 week after the last GVAX/Placebo vaccine, at the discretion of the transplant physician, with the goal to be off immune suppression by 6-9 months in the absence of GVHD.
- 5.2.4.2 **Tacrolimus taper for patients with progressive disease before completion of vaccinations**: Patients with evidence of progressive disease AND requiring additional therapy or taper of immune suppression will receive no further vaccinations. In these cases, the tacrolimus taper will be performed at the discretion of the treating physician.

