12.0 STATISTICAL CONSIDERATIONS

12.1 Endpoints

12.1.1 **Primary Endpoint**: The primary endpoint of this study is progression-free survival (PFS) at 18 months post-randomization. Progression-free survival is defined as time from randomization to progression of disease or death whichever occurs first. Patients with relapse/progressive disease who re-enter remission after vaccination or upon withdrawal of immune suppression alone will not be considered as having disease progression. The primary analysis will be performed using the modified intention-to-treat (ITT) principle, i.e., all transplanted and eligible patients who receive at least one vaccination will be included in the analysis according to the treatment arm they are randomized to.

12.1.2 **Secondary Endpoints**

- 12.1.2.1 Safety and toxicity of vaccination, as measured by the development of:
 - Grade II-IV and III-IV acute GVHD
 - CTC grade \geq 3 non-hematologic toxicity, or

- Grade \geq 4 hematologic toxicity attributable to vaccination
- 12.1.2.2 Biologic responses to vaccination following allogeneic stem cell transplant, as assessed by laboratory and histologic analyses of blood before and after vaccination, and skin biopsy samples at vaccination sites (Section 8.0). Serum and circulating mononuclear cells will be frozen prior to beginning vaccination and at regular intervals thereafter. Bone marrow aspirates will also be cryopreserved, if sufficient material is available.

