12.2 Study Design and Objectives

This is a randomized placebo controlled Phase II study of GVAX versus placebo vaccination given early after allogeneic HSCT in high risk AML/MDS patients. The premise is that GVAX vaccination early after HSCT will increase progression-free survival (PFS) in this patient population. The target accrual goal is 106 eligible patients for vaccination, 53 per each arm, over a 3.8 year period and followed for an additional 18 months. This design will give approximately 80% power to detect a 75% increase in 18 month PFS in the GVAX arm (Arm A) compared to the placebo arm (Arm B) as graphically illustrated in Figure 1.

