12.5 Sample Size and Power Calculations

In our previous study¹⁰, the 2-year progression-free survival for 15 patients who received at least one vaccination was 46%. This estimate compared to 18% 2-year PFS from our contemporaneous control cohort that was most similar to those patients in the GVAX trial. Extrapolating this information, we hypothesize that the PFS will be increased by 75% at 18 months post randomization in Arm A (GVAX) compared to Arm B (placebo). A retrospective analysis of high risk AML/MDS patients who underwent myeloablative or RIC HSCT between 2004 and 2008 at DFCI shows that a small portion of patients are cured from the underlying disease after allogeneic HSCT and the distribution of PFS follows a two-component exponential cure rate model (Figure 1). Basing the fitted curve in Figure 1 as the null hypothesis, we hypothesize that the PFS will be increased by 75% from 26% to 46% by 18 months post HCT in Arm A. More specifically, the proposed alternative hypothesis is H_A: S_A > S_B,

where S_A and S_B denote the distributions of PFS in Arms A and B, as shown in (1) and (2), respectively

$$\begin{split} S_A &= 0.45 + 0.45 * exp(-t*(log(2)/2.5)) + 0.1*exp(-t*(log(2)/4.5)) \ (1) \\ S_B &= 0.24 + 0.76 * exp(-t*(log(2)/3.5)) \end{split} \tag{2}$$

This projection incorporates approximately 30-45 days of wait time from randomization to the start of GVAX/Placebo vaccination and additional ~40 days for the administration of a serial of 6 vaccinations. During this period, we expect little difference in PFS between two arms. Figure 4 depicts (1) and (2) graphically. With this design, 106 eligible patients with 69 events will be required to achieve approximately 80% power with one-sided significance level of 0.15. Since this is a direct but nondefinitive randomized comparison to a standard treatment control, we follow recommendations made by Rubinstein et al. ^{18, 19} and use a one-sided type I error rate of 0.15 with 80% power ¹⁸⁻²⁰. The power calculation is calculated using the R program, *Powlgrnk* (developed by [name] at DFCI), which computes power of the two-group log-rank test for arbitrary failure time distributions and has been used for non-proportional hazards alternative.²¹

[figure not shown]

Figure 4. Target PFS. Blue line represents the projected PFS distribution in Arm A (GVAX) and red line represents the projected PFS distribution in Arm B (Placebo). The solid black line is the Kaplan-Meier curve from the historical control

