12.6 Interim Analyses

The study will be monitored using standard procedures and processes by an independent Data and Safety Monitoring Committee (DSMC) of the Dana-Farber Harvard Cancer Center (DF/HCC). Interim analysis for efficacy will occur annually starting at 33% information time, which is anticipated to occur approximately 2.8 years after the start of the trial. The interim results will be reported to the DF/HCC DSMB annually. However, these interim inspections will not have an effect in terms of

stopping accrual to the study and terminate the study early in favor of alternative (superiority) or null hypothesis (futility). This is because i) due to a small sample size at each interim look, stopping early for futility would result in substantially wide confidence intervals, larger Type II error, and thus leading to greater uncertainty about the magnitude of the PFS difference, ii) even if the PFS difference is not as large as targeted, investigators are interested in learning the magnitude of the PFS difference for further investigation, iii) stopping early for superiority would provide less safety data than planned and potential difficulty with the efficacy analysis and its interpretation.

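### Section 6.4 allows unblinding once the last vaccination is given, roughly 12 to 16 months before the last 18-month PFS endpoint, and does not say who is unblinded

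*Combined protocol and SAP*

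**What the plan says.** Section 6.4 says that no unblinding is planned while patients are on treatment and provides for case-by-case unblinding when a patient's care requires it. It then adds: "After the study is closed to accrual and the last patient has completed the GVAX/placebo vaccinations, the study may be unblinded for data analysis".

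Section 1.1 masks the patients and the treating "physicians, nurses, research staff, and data assessors". Section 4.2 sends the assignment to the cell manufacturing facility and keeps all other study personnel blinded. Neither section says when masking ends.

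The primary endpoint (section 12.1.1) is PFS at 18 months after randomization. Section 12.2 plans accrual "over a 3.8 year period and followed for an additional 18 months". Section 12.5 states the timing behind the design: "This projection incorporates approximately 30-45 days of wait time from randomization to the start of GVAX/Placebo vaccination and additional ~40 days" for the six vaccinations.

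Three other provisions bear on the period after the last vaccine:

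- Section 5.2.4.1, on tacrolimus: "Taper may commence 1 week after the last GVAX/Placebo vaccine, at the discretion of the transplant physician". Section 1.1 adds the aim, "with the goal to be off immune suppression by 6-9 months post transplant in the absence of GVHD".
- Section 12.1.1, on the event definition: "Patients with relapse/progressive disease who re-enter remission after vaccination or upon withdrawal of immune suppression alone will not be considered as having disease progression".
- Section 12.6, on early arm-level results: "The interim results will be reported to the DF/HCC DSMB annually".

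**The concern.** The trigger in section 6.4 is the end of accrual and vaccination, whereas the primary endpoint matures 18 months after the last randomization. The clause may be meant for analysts only, but it does not say so, and no other section limits it.

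Masking still has work to do after the last vaccine. The timing and pace of the tacrolimus taper are left to the physician and can begin one week later. A relapse that remits on withdrawal of immune suppression alone does not count as a PFS event, so a discretionary act can bear on whether an event is counted. The protocol states no progression criteria and no blinded adjudication, which leaves masking of assessors as the stated protection. Secondary outcomes are exposed too: the chronic GVHD survey is scored by the provider and accepts subjective symptoms, and adverse events, with judged attribution, are collected to 18 months after transplant.

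**Working it through.** **The plan's own figures.** With S_A and S_B from section 12.5, S_A(18) = 45.9% and S_B(18) = 26.2%, matching the stated 46% and 26%. Even accrual over 3.8 years plus 18 months of follow-up gives 69.2 expected events (stated: 69). Simulating the log-rank test at one-sided 0.15 gives 81.3% power (stated: about 80%). The curves can therefore be used to size the exposure. The plan gives no figure for the gap between unblinding and the last endpoint.

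**Inputs.**
- 106 patients over 3.8 years = 45.6 months, so 106 / 45.6 = 2.325 patients per month (section 12.2).
- Randomization to first vaccine: 30 to 45 days; vaccination course: about 40 days (section 12.5).
- The schedule in section 1.1 puts doses on days 0, 7, 14, 28, 42 and 56, so the course is 56 days from first to last dose.
- The interval from randomization to transplant is not given. Waits of 1.25 to 4 months from randomization to first vaccine are assumptions.

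**Formulas.** Let d = months from randomization to last vaccine (days / 30.44) and S = (S_A + S_B)/2.
- Gap = 18 − d
- Patients short of 18 months = 2.325 × (18 − d)
- Of these, event-free = 2.325 × ∫ S(t) dt from d to 18
- Events still to come = 2.325 × ∫ [S(t) − S(18)] dt from d to 18
- Events expected by month 18 = 53 × (1 − 0.459) + 53 × (1 − 0.262) = 67.8, using unrounded S values

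| Wait + course | Gap (months) | Patients short of 18 months | Event-free | Events to come (share of 67.8) |
|---|---|---|---|---|
| 30 + 40 days | 15.70 | 36.5 | 16.8 | 3.61 (5.3%) |
| 45 + 40 days | 15.21 | 35.4 | 15.9 | 3.20 (4.7%) |
| 1.25 months + 56 days | 14.91 | 34.7 | 15.5 | 2.97 (4.4%) |
| 2.5 months + 56 days | 13.66 | 31.8 | 13.6 | 2.17 (3.2%) |
| 4 months + 56 days | 12.16 | 28.3 | 11.6 | 1.46 (2.2%) |

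The first two rows rest on section 12.5 alone; the last three use assumed waits. The gap drops below 12 months only if the wait exceeds 6 − 56/30.44 = 4.16 months.

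**Taper route.** Vaccination starts on day +30 to +60 and lasts 56 days, so the last vaccine falls on day 86 to 116 after transplant (2.83 to 3.81 months). The time left to the 6-to-9-month goal is 6 − 3.81 = 2.19 months to 9 − 2.83 = 6.17 months. At 2.325 per month that is 5.1 to 14.4 patients. Of these, 2.4 to 7.8 are event-free, assuming 0 to 3 months from randomization to transplant.

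**Scale.** One event moves an arm's 18-month PFS by 1/53 = 1.9 points. The standard error of the difference is √(0.26 × 0.74/53 + 0.46 × 0.54/53) = 0.091, or about 9 points, against a 20-point target.

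**The case against.** The strongest reply is that section 6.4 sets an earliest date and a purpose, not a plan to unblind early. The primary analysis needs 18-month data, so unblinding for that analysis would naturally come after follow-up. Sections 1.1 and 4.2 set general masking, and an exception for data analysis does not naturally extend to patients or treating clinicians. This is a reasonable reading, but the text does not commit to it. If it is the intended meaning, saying so costs nothing.

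The effect is also small. Split by arm, the table's range of 1.46 to 3.61 remaining events is about 0.5 to 1.3 on GVAX and 1.0 to 2.3 on placebo. If every remaining GVAX event went uncounted, that arm's 18-month PFS would rise by 0.9 to 2.5 points. Wrong progression calls among the event-free patients are a separate route that this does not measure. Room for judgement is limited as well: death is part of the endpoint, and section 9.0 schedules marrows one month after the last vaccine and at 12 and 18 months, with flow cytometry, cytogenetics and chimerism. These points stand and limit the severity.

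Finally, the blind may already be imperfect. Placebo is saline, and in the pilot the vaccine produced local skin reactions in the 14 assessable patients. That is a fair caution about how much extra bias section 6.4 would add. But inferring the arm from a skin reaction is weaker than being given the code, and the sponsor masks the syringes, so it evidently values the blind.

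**Conclusion.** The concern holds. Section 6.4 states a rule whose trigger comes too early for the primary endpoint, and nothing elsewhere supplies an end date for masking or restricts who may be unblinded.

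The gap is 15.2 to 15.7 months on section 12.5's timing. The lower end of the 12-to-16-month range depends on an assumed wait of up to 4 months, because the randomization-to-transplant interval is not documented. The patient and event counts assume even accrual and the design's PFS curves.

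About 2 to 5% of PFS events are exposed, which is modest for a phase II trial that calls its comparison nondefinitive. The plan provides for possible early disclosure; it does not show that clinicians or assessors would receive the codes. The matter merits correction as an inexpensive safeguard of the primary endpoint, with medium confidence about its practical effect.

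**What to change.** Reword section 6.4 in two or three sentences:

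- Patients, treating clinicians, site staff and outcome assessors stay masked until the last randomized patient has reached the 18-month endpoint and the PFS data are locked.
- The existing exception for unblinding needed for a patient's care is kept.
- Before that point, arm-level data go only to the DSMB and its reporting statistician and, if needed, to laboratory analysts with no part in care or outcome assessment.

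The cost is that investigators wait about 12 to 16 months longer for arm-level correlative results (section 12.9) and safety comparisons. Allowing access by uninvolved laboratory analysts reduces the effect on correlative work, and the DSMB route for interim results is unchanged. The primary analysis is not delayed, since it needs the 18-month data.
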